Nonclinical cardiovascular toxicity findings that could potentially be relevant to the clinical use of AVXS-101 have been reported in 2 mouse toxicology studies of AVXS-101. Similar findings were reported in both studies. Findings in the ventricles of the heart were comprised of inflammation, edema and fibrosis. Primary findings in the atrium of the heart were thrombosis and inflammation. The underlying mechanism of these findings and the translatability of the observed findings in mice to primates are not known at this time.

The available clinical cardiovascular safety data have not provided evidence for a cardiovascular safety problem in humans. As of the last update to the Investigator's Brochure (v5), there have

been no cardiovascular AEs that have been judged to be related to AVXS-101 in the clinical studies.

A transient decrease in platelet counts has been observed with both IV and less frequently with IT administration. The majority of values remained above the lower limit of normal. Decreases were clinically asymptomatic and transient.

This risk can be effectively managed through monitoring platelet counts for 1 month following dosing, and appropriate prednisolone (or an equivalent corticosteroid in countries where prednisolone is not available) use.

Preclinical data indicate that in most cases, DNA delivered by recombinant AAV vectors predominantly persists as extrachromosomal elements (episomes) rather than integrating into host cell genomes ([McCarty 2004](#)). Although AVXS-101 is also not anticipated to integrate into the host cell genome as described above, the long-term consequences of administering AAV viral vectors to humans are not yet fully understood. This is in contrast to wtAAV, also nonpathogenic, which has the ability to stably integrate into the host cell genome at a specific site (designated AAVS1) in the human chromosome 19 ([Kotin 1990; Surosky](#) ). Since the AVXS-101 product uses AAV9 with all of the wtDNA removed from the capsids, except for the inverted terminal repeats (ITRs), the potential risk of incorporation of AVXS-101 into the patient chromosomal DNA is thought to be significantly reduced.

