#### **4.8.1.4. Electrocardiogram (ECG)**

Standard 12-lead ECGs will be performed at screening/baseline, Day 1, Day 2, Day 3, Month 3, Month 6, Month 9, Month 12, and Month 15 (Cohort 3 only) visits (or Early Termination) including heart rate, PR, QRS, QTcF. 12-lead ECG will also have QR included. 12-lead ECG tracings will be interpreted locally; however, the tracings will be submitted to a centralized interpreter for inclusion in the study dataset. Only descriptive statistics are planned for this data.

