## 11.5. Vital Signs

Vital signs will include blood pressure, respiratory rate, pulse, heart rate, pulse oximetry and axillary temperature. Body weight and length and/or height will also be collected.

Vital signs will be examined at each scheduled visit and time point. The baseline value will be the last measurement before date and time of the injection of study drug. Mean changes from baseline to each post-baseline visit and time point will be summarized with the baseline mean, visit/time point mean, change from baseline mean, standard deviation, minimum, maximum, and median. Summaries will be presented overall and by actual dose received and age group.

In addition, vital signs results will be flagged as PCS if they meet the pre-specified criteria which are defined outside of this SAP. The number and percent of patients meeting each PCS criterion at each scheduled visit and time point will be summarized overall and by actual dose received and age group. For body weight, the PCS criteria are based on percentile weights for age and sex as defined by the World Health Organization Child Growth Standards. These definitions extend

through 60 months of age. If a patient is >60 months of age at the time of their weight assessment, they will not be assessed for PCS weight values.

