## 11.6. ECG

A 12-lead ECG will be conducted at scheduled visits of Screening/Baseline, Day 1, Day 2, Day 3, Month 3, Month 6, Month 9, and Month 12 (or Early Termination), and assessed by a central reviewer. The baseline value will be the last measurement on or before the day of injection of study drug. Mean changes from baseline, standard deviation, minimum, maximum, and median to End of Study/Early Termination visit will be summarized for HR, PR, QR, QRS, QTcF as measured by the central reviewer.

The central reviewer will identify abnormal ECGs that are PCS, the definitions for which are maintained outside of this document.

A listing of all PCS ECGs will be provided. Summaries of ECG data will be presented overall and by actual dose received and age group.

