## 11.7. 12-Lead Holter Monitor

Patients will have a 12-lead continuous Holter monitor attached 24 hours prior to dose administration on Day -1 and the Holter will remain in place through 48 hours post-dose (Day 3). Serial ECG data from Holter monitor will be pulled in triplicate at time points of 'pre-dose', '2 hour', '4 hour', '6 hour', '8 hour', '12 hour', '24 hour', '36 hour' and '48 hour' post-dose and assessed by a central reviewer. The triplicate of each parameter for HR, PR, QRS, QTcF, as measured by the central reviewer, at each time point will be averaged for summaries. The summaries of Holter monitor data will be done by the actual treatment received overall and by dose and age group.

Twenty-four-hour Holter monitoring will also be performed as per the Schedule of Assessments.

The central reviewer will identify abnormal ECGs that are PCS based on central reviewing guidelines provided by BMS. The number and percent of patients meeting each PCS criterion will be summarized starting at '2 hour' and continuing through '48 hour'.

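### SAP 11.6 plans no change-from-baseline table and no count of potentially clinically significant findings for the 12-lead ECGs at Months 3, 6 and 9, or at Month 12 for Dose C

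*SAP*

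**What the plan says.** SAP 4.8.1.4 schedules 12-lead ECGs at screening, on Days 1, 2 and 3, at Month 3, and then at "Month 6, Month 9, Month 12, and Month 15 (Cohort 3 only) visits (or Early Termination) including heart rate, PR, QRS, QTcF". Section 11.6 repeats this schedule without Month 15.

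The analysis in 11.6 has two parts. The first is a change summary tied to one visit, for HR, PR, QR, QRS and QTcF: "Mean changes from baseline, standard deviation, minimum, maximum, and median to End of Study/Early Termination visit will be summarized". The second is "A listing of all PCS ECGs will be provided". Summaries are to be given overall, by actual dose and by age group. The PCS definitions are kept outside the SAP.

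Section 11.7 covers ECGs extracted in triplicate from the Holter recording, from pre-dose to 48 hours: "The triplicate of each parameter for HR, PR, QRS, QTcF, as measured by the central reviewer, at each time point will be averaged for summaries". It also plans PCS counts and percentages from 2 to 48 hours.

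For vital signs, 11.5 is broader than 11.6: "Mean changes from baseline to each post-baseline visit and time point will be summarized", with PCS counts at each visit and time point. Section 11.4.2 likewise gives laboratory change at each post-baseline visit and PCS counts by dose and age group.

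**The concern.** The protocol treats the heart as an organ to watch. Protocol 5.5 states that "Nonclinical cardiovascular toxicity findings that could potentially be relevant to the clinical use of AVXS-101 have been reported". Protocol 5.3 names heart and liver as the main target organs in the three-month mouse studies (intravenous dosing), and SAP 11.3.2.4 makes cardiac events an adverse event of special interest.

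ECGs are collected and centrally read through follow-up, yet 11.6 turns only the last one into a table. An interval change that appears at Month 3 or 6 and resolves by the last visit would enter no specified ECG table. If it met the PCS definition it would appear in a listing, with no count or denominator by dose. If it fell short of that definition, no named ECG output would show it.

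The tabulated visit also falls at different times: Month 12 for Doses A and B, Month 15 for Dose C, and earlier for anyone who terminates early. The dose columns therefore describe different lengths of follow-up.

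**Working it through.** No power or sample size figure is involved. The check is a count of visits and a comparison of sections.

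**Step 1. Scheduled ECGs after the 48-hour window** (SAP 4.8.1.4; SAP 19.2)
- Doses A and B: Months 3, 6, 9 and 12 = 4 visits.
- Dose C: Months 3, 6, 9, 12 and 15 = 5 visits.

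**Step 2. Visits with a change table under 11.6**
- Doses A and B: Month 12 only, so 4 − 1 = 3 have none (Months 3, 6, 9).
- Dose C: Month 15 only, so 5 − 1 = 4 have none (Months 3, 6, 9, 12).

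Days 1 to 3 are left out of this count because 11.7 summarises the same period. Whether the Day 1 ECG is a baseline or a post-dose record is unclear: 11.6 takes the last value on or before the injection day, while 6.5 takes the latest value before Day 1. The counts above do not depend on that.

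**Step 3. Side by side**

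| Data | Change from baseline shown at | PCS output |
|---|---|---|
| Laboratory (11.4.2) | each post-baseline visit | number and % |
| Vital signs (11.5) | each visit and time point | number and % |
| Holter-extracted ECG (11.7) | parameters summarised at each time point to 48 h (change not specified) | number and %, 2 to 48 h |
| 12-lead ECG (11.6) | End of Study/Early Termination only | listing |

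**Step 4. Does another section fill Months 3 to 9?**
- Section 6.5 names ECGs and says change analyses use the scheduled-visit value and PCS summaries use all values. That settles which value enters an analysis; it does not create a by-visit table.
- Section 4.8.1.4 says only that descriptive statistics are planned.
- 24-hour Holters are repeated at Months 3, 6 and 9 (4.8.1.6), but the parameter summaries and PCS counts spelled out in 11.7 stop at 48 hours.
- Echocardiogram results are listed (11.10).

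**Step 5. Interval at the tabulated visit.** SAP 7.1 places Month 12 at Day 360 and Month 15 at Day 450. The scheduled gap between the dose columns is 450 − 360 = 90 days, before Early Termination values are added.

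**Step 6. What added tables could show.** One child with a PCS ECG is 1/3 = 33% of the planned Dose A group, 1/4 = 25% of the children treated at Dose C (SAP 2.2.1), and 1/12 = 8% of one Dose B age group as planned. Children enrolled before Amendment 5 may lack earlier ECGs, so denominators will vary by visit.

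**The case against.** The strongest reply is that cardiac safety is far from unmonitored. Most of it stands:

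- A reader might infer from 11.6 that every ECG before the last has no summary. That is wrong. Section 11.7 summarises HR, PR, QRS and QTcF at each extraction time to 48 hours, with PCS counts. An immediate effect would be caught there.
- Heart rate is tabulated by visit with the vital signs. CK-MB or troponin I is a chemistry variable with by-visit change and PCS counts. Cardiac adverse events are tabulated by dose. Protocol 12.7 has each ECG read locally for immediate safety and again centrally.
- A reader might tie the gap to the primary safety endpoints. SAP 4.4 defines those as adverse event categories; ECG comes under additional safety endpoints in 4.8.
- A reader might argue that growth over 12 to 15 months distorts the raw change, so age-specific limits are needed. The documents give no ECG values by age, so no drift can be sized, and the external PCS definitions may already allow for age. That remedy is not supported here.
- A reader might say the last visit is the one least likely to show harm. The documents do not establish when an effect would occur. Protocol 5.5 describes inflammation, edema, fibrosis and thrombosis in mice and reports no evidence of a cardiovascular safety problem in humans.
- The table shells are in a separate document (SAP 18) and may include a by-visit ECG table.

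None of this gives the PR, QRS or QTcF intervals a specified table at Months 3, 6 and 9, or at Month 12 for Dose C. The SAP should state the analysis itself rather than leave it to shells.

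**Conclusion.** The point holds in limited form. Read as written, 11.6 is narrower than 11.4.2 and 11.5, and it leaves the middle of follow-up without an ECG interval summary or a PCS count. The size is three of four post-48-hour visits at Doses A and B and four of five at Dose C. The tabulated visit also differs by 90 scheduled days between doses. This is a gap in reporting data already collected. It does not show that a cardiac effect exists or would be missed clinically.

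The conclusion assumes that the specific wording of 11.6 governs over the general rule in 6.5, and that no unseen shell adds the missing table. The gain is a clearer view of a delayed or transient change, mainly at Dose B, where 24 children were planned. At Doses A and C the tables will be sparse and descriptive only.

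**What to change.** Amend SAP 11.6 to:

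1. summarise change from baseline in HR, PR, QR, QRS and QTcF at each scheduled 12-lead ECG visit, by actual dose and age group, with the number of children at each visit;
2. show Month 12 for all doses and Month 15 separately for Dose C, adding Month 15 to the schedule in 11.6;
3. add the number and percentage of patients with any post-baseline PCS ECG, by dose and age group, and keep the listing.

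The same edit should reconcile the ECG baseline rule in 11.6 with that in 6.5, so that a by-visit table has one reference value. The cost is SAP wording and one or two descriptive tables from ECGs already read centrally. No new assessment is needed, and no clinical rule changes.

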## 11.7. 12-Lead Holter Monitor

Patients will have a 12-lead continuous Holter monitor attached 24 hours prior to dose administration on Day -1 and the Holter will remain in place through 48 hours post-dose (Day 3). Serial ECG data from Holter monitor will be pulled in triplicate at time points of 'pre-dose', '2 hour', '4 hour', '6 hour', '8 hour', '12 hour', '24 hour', '36 hour' and '48 hour' post-dose and assessed by a central reviewer. The triplicate of each parameter for HR, PR, QRS, QTcF, as measured by the central reviewer, at each time point will be averaged for summaries. The summaries of Holter monitor data will be done by the actual treatment received overall and by dose and age group.

Twenty-four-hour Holter monitoring will also be performed as per the Schedule of Assessments.

The central reviewer will identify abnormal ECGs that are PCS based on central reviewing guidelines provided by BMS. The number and percent of patients meeting each PCS criterion will be summarized starting at '2 hour' and continuing through '48 hour'.

## 11.8. Physical Examination

Shift tables summarizing the shift of physical examination results ('Normal', 'Abnormal Not Clinically Significant', 'Abnormal Clinically Significant') in head, eyes, ears, nose and throat, lungs/thorax, cardiovascular, abdomen, musculoskeletal, neurologic, dermatologic, lymphatic, and genitourinary from baseline to post-baseline visits will be presented. A table summarizing observed and change from baseline values for head circumference will be produced.

A listing of physical examination findings (normal or abnormal) will be provided.

## 11.9. Pulmonary Exam

Patients will be assessed by a pulmonologist at the time points specified in the Schedule of Assessments on of the pulmonologist and/or investigator.

Pulmonary exam results will be presented in a listing.

### **11.10. Echocardiogram**

Echocardiograms will be conducted at the time points specified in the Schedule of Assessments. Echocardiograms will be interpreted locally and results from the local interpretation (abnormal/normal, etc.) will be captured in the eCRF.

Additionally, echocardiogram data will be provided to an external cardiologist for centralized review; this will be considered the primary echocardiogram source data.

Clinically significant, treatment-emergent findings may be reported as AEs. A listing of echocardiogram results (abnormal/normal, etc.) and findings (left ventricle function, patent foramen ovale, or other) will be provided for all screening and post-baseline visits.

### **11.11. Ventilatory support**

The number of hours per day of non-invasive positive pressure ventilator in the intervals between each post-baseline visit will be summarized overall and by dose and age group using descriptive statistics. Ventilatory support data will not be compared with the PNCR natural history cohort as that data was not collected and is not available for comparison.

### **11.12. Vector Shedding**

Saliva, urine, and stool samples will be collected for vector shedding in accordance with the Schedule of Study Assessments, which includes 24 hours (Day 2) and 48 hours (Day 3) post-dose. Patients at all sites  $\geq$  48 months who are no longer in diapers will provide full volume urine and full volume feces samples at Day 7, Day 14, and Day 30 for at least one void and one defecation. A subset of patients at sites opting to participate in the vector shedding sub-study will have 24-hour total volume urine and fecal samples collected through 24 hour-post dose and 48 hours-post dose.

Descriptive statistics of mean, standard deviation, minimum, maximum, and median on volume of saliva, urine and feces at each scheduled visit will be summarized. A listing of vector shedding will be provided. Vector shedding data will not be compared with the PNCR natural history cohort as that data was not collected and is not available for comparison.

### **11.13. Values of Clinical Concern**

Not applicable for this SAP.

## **12. HEALTH ECONOMICS**

Not applicable for this SAP.

## **13. INTERIM SAFETY REVIEWS**

Up to three (3) safety reviews by the DSMB will be conducted. The DSMB will review the safety data extract from the database. The safety analysis specified in this SAP is not planned for the DSMB.

The first DSMB interim safety review will take place after three (3) participants in Cohort 1 have been dosed. The consideration for this review is terminating the study for safety. In the absence of a termination recommendation, a recommendation to escalate enrollment to the higher dose is made.

The second DSMB interim safety review will take place after three (3) participants in Cohort 2 have been dosed (6 total dosed). The consideration for this review is terminating enrollment in Cohort 2 due to safety concerns. In the absence of a termination recommendation, a recommendation to expand the current Cohort 2 is made.

The third DSMB interim safety review may take place after three (3) patients have been enrolled in Cohort 3. The consideration for this review is terminating enrollment in Cohort 3 due to safety concerns. In the absence of a termination recommendation, a recommendation to expand the current Cohort 3 is made.

#### **14. CHANGE FROM ANALYSIS PLANNED IN PROTOCOL**

Final

## 16. PROGRAMMING CONSIDERATIONS

See TLF Documentation for Details.

## 17. QUALITY CONTROL

SAS programs are developed to produce output such as analysis data sets, summary tables, data listings, figures or statistical analyses. The CRO's SOPs provide an overview of the development of such SAS programs.

The CRO's SOPs describe the quality control procedures that are performed for all SAS programs and output. Quality control is defined here as the operational techniques and activities undertaken to verify that the SAS programs produce the output by checking for their logic, efficiency and commenting and by review of the produced output.

For all data sets, tables and listings generated by SAS, the CRO will create SAS codes independently, and then use SAS PROC COMPARE procedure to perform 100% electronic comparison for all numerical and character values. In addition, the Lead Biostatistician, Lead Programmer and Senior Statistical Reviewer will review all Tables, Listings, and Figures (TLFs) for consistency and accuracy.

[figure not shown]
[figure not shown]
Deliveries of datasets, SAS programs, and output from the CRO to AveXis will occur via a secure file transfer platform.

## 18. MOCK-UPS

Refer to TLF Mock-ups which are maintained in a separate document.

## 19. APPENDICES

### 19.1. Hammersmith Functional Motor Scale - Expanded

Smartnet & PNCR		Hammersmith Functional Motor Scale for SMA (HFMS)					07/03/09
Name	DOB	Time taken to complete					
Date of assessment		Evaluator					
Date of spinal surgery							
Please circle highest current level of independent mobility							LBC = Limited by contracture
None	Rolls	Bottom shuffles	creeps /crawls	Walks with crutches / frame /rollator	Walks with KAFO's / AFO's	Independent walking	
Comment.....							
Test	Instruction	2	1	0	L B C	Comments S = score	
1 Plinth /chair sitting Can be over edge of plinth or on plinth / floor. Record best you see	Can you sit on the plinth /chair without using your hands for support for a count of 3? Back unsupported (feet +/- support)	Able to sit using no hand support for a count of 3 or more	Needs one hand support to maintain balance for a count of 3	Needs two hand support to maintain balance		Item 1 Predominant spinal posture 	
2 Long sitting Legs straight = knees maybe flexed, knee caps pointing upwards, ankles <10cm apart	Can you sit on the floor/plinth without using your hands for support and with your legs straight for a count of 3?	Able to sit on floor/plinth with legs straight without hand support for a count of 3	Able to sit on floor/plinth with legs straight propping with one hand support for a count of 3	Able to long sit using two hands for a count of 3 Or unable to sit with straight legs		Predominant leg posture 	
3 One hand to head in sitting Hand touch head above level of ears	Can you get one hand to your head without bending your neck	Able to bring one hand to head. Head and trunk remain stable	Can only bring hand to head by flexing head	Unable to bring hand to head even using head and trunk movement		R / L	
4 Two hands to head in sitting Hands touch head above level of ear	Can you lift both hands up at the same time, to your head, without bending your neck?	Able to place both hands on head arms free from side. Head and trunk remain stable	Able to place hands on head but only using head flexion or side tilt or crawling hands up or one at a time	Unable to place both hands on head			
5 Supine to side-lying	Can you roll onto your side in both directions? Try not to use your hands	Able to ½ roll from supine both ways	Can ½ roll only one way R / L	Unable to half roll either way		Shoulders perpendicular to floor. Trunk and hips in line with body	
6 Rolls prone to supine over R	Can you roll from your tummy to your back in both directions?	Turns to supine with free arms to the right	Turns to supine using arms to push/ pull with	Unable to turn into supine			
7 Rolls prone to supine over L		Turns into supine with free arms to the left	Turns to supine using arms to push/ pull with	Unable to turn into supine			
8 Rolls supine to prone over R	Can you roll from your back to your front in both directions?	Turns to prone with free arms to the right	Turns to prone by pulling/ pushing on arms	Unable to turn into prone			
9 Rolls supine to prone over L		Turns to prone with free arms to the left	Turns to prone by pulling/ pushing on arms	Unable to turn into prone			
10 Sitting to lying	Can you lie down in a controlled way from sitting?	Able to lie down in a controlled fashion through side lying or using clothes	Able to lie down by flopping forwards and rolling sideways	Unable or falls over			
11 Props on forearms	Can you prop yourself on your forearms and hold for a count of 3?	Able to achieve prop on elbows with head up for a count of 3	Holds position when placed for a count of 3	Unable			
12 Lifts head from prone	Can you lift your head up keeping your arms by your side for a count of 3?	Able to lift head up in prone arms by side for a count of 3	Lift head with arms in a forward position for a count of 3	Unable			
13 Prop on extended arms	Can you prop yourself up with straight arms for a count of 3?	Able to prop on extended arms, head up for a count of 3	Can prop on extended arms if placed for a count of 3	Unable			
14 Lying to sitting	Can you get from lying to sitting without rolling to your tummy?	Able by using side lying	Turns into prone or towards floor	Unable			
15 Four-point kneeling	Can you get onto your hands and knees with your head up and hold for a count of 3?	Achieves four-point kneeling – head up for a count of 3	Holds position when placed for a count of 3	Unable			

Test	Instruction	2	1	0	L B C	S =	Comments S = score
16 Crawling	Can you crawl forwards?	Able to crawl forwards – moves all four points twice or more	Moves all four points only once	Unable			
17 Lifts head from supine	Can you lift your head to look at your toes keeping your arms folded for a count of 3?	In supine, head must be lifted in mid-line. Chin moves towards chest. Held for a count of 3	Head is lifted but through side flexion or with no neck flexion. Held for a count of 3	Unable			
18 Supported standing	Can you stand using one hand for support for a count of 3?	Can stand using one hand support for a count of 3	Able to stand with minimal trunk support (not hip) for a count of 3	Can stand with hand support but needs knee/hip support in addition for a count of 3  Or unable			
19 Stand unsupported	Can you stand without holding onto anything for a count of 3?	Can stand independently for the more than a count of 3	Stands independently for a count of 3	Stands only momentarily (less than a count of 3)  Or unable			
20 Stepping	Can you walk without using any help or aids? Show me	Able to take more than 4 steps unaided	Able to take 2 – 4 steps unaided	Unable			
SCORE		No of 2's =	No of 1's =	No of 0's =	TOTAL = /40		
Comments							

PNCR		Expanded Hammersmith Functional Motor Scale for SMA (HFMSE)			add-on module			07/03/09
Test	Instruction	2	1	0	L B C	S	Comments S = score	
21 Right hip flexion in supine	Can you bring your right knee to your chest?	Full hip flexion achieved	Initiates right hip and knee flexion (more than 10% of available range of motion)	Unable				
22 Left hip flexion in supine	Can you bring your left knee to your chest?	Full hip flexion achieved	Initiates left hip and knee flexion (more than 10% of available range of motion)	Unable				
23 High kneeling to right half knee	Can you bring your left leg up so that your foot is flat on the ground without using your arms and hold for a count of 10?	Arms used for transition, maintains arms free in half knee for a count of 10	Maintains half knee with arm support for a count of 10	Unable				
24 High kneeling to left half knee	Can you bring your right leg up so that your foot is flat on the ground without using your arms and hold for a count of 10?	Arms used for transition, maintains arms free in half knee for a count of 10	Maintains half knee with arm support for a count of 10	Unable				
25 High kneeling to stand leading with left leg	Can you stand up from this position starting with your left leg without using your hands? May need demonstration	Able with arms free	Able to shift weight off both knees (with or without arm support)	Unable				
26 High kneeling to stand leading with right leg	Can you stand up from this position starting with your right leg without using your hands? May need demonstration	Able with arms free	Able to shift weight off both knees (with or without arm support)	Unable				
27 Stand to sit	Can you sit on the floor, in a controlled way? Try not to use your arms.	Able to sit down with arms free and no collapse	Sits on floor but uses arms or crashes	Unable				
28Squat	Can you squat? Pretend you are going to sit in a very low seat.	Squats with arms free (at least 90° of hip and knee flexion)	Initiates squat (more than 10%), uses arm support	Unable to initiate				
29 Jump 12" forward	Can you jump as far as you can, with both feet, from this line all of the way to the other line?	Jumps at least 12", both feet simultaneously	Jumps between 2-11", both feet simultaneously	Unable to initiate jump with both feet simultaneously				
30 Ascends stairs with rail	Can you walk up the steps? You can use one railing	Ascends 4 stairs with railing, alternating feet	Ascends 2-4 stairs, one rail, any pattern	Unable to ascend 2 stairs one rail				
31 Descends stairs with rail	Can you walk down the steps? You can use one railing	Descends 4 stairs, with railing, alternating feet	Descends 2-4 stairs, one rail, any pattern	Unable to descend 2 stairs with one rail				
32 Ascends stairs without rail	Can you walk up the steps? This time try not to use the railing	Ascends 4 stairs, arms free, alternating feet	Ascends 2-4 stairs, arms free, any pattern	Unable to ascend 2 stairs arms free				
33 Descends stairs without rail	Can you walk down the steps? This time try not to use the railing	Descends 4 stairs, arms free, alternating feet	Descends 2-4 stairs, arms free, any pattern	Unable to descend 2 stairs arms free				
SCORE		No of 2's =	No of 1's =	No of 0's =			TOTAL = /66	

